## Memorial Sloan-Kettering Cancer Center IRB Protocol

**IRB#: 07-029A(6)**

counts were compared between treated and untreated nevi. Complete response was defined as reversion to clinically normal appearing skin. Partial response was defined as a 50% or greater reduction in diameter and progression was defined as a 50% or greater increase in diameter.

### 13.0 CRITERIA FOR REMOVAL FROM STUDY

In the event that the treated lesion changes in a clinically worrisome fashion with correlating histology demonstrating invasive carcinoma during the study, the patient will be removed from the study. Patients who have unacceptable toxicities will be removed from the study. Unacceptable toxicities consist of headache, influenza-like symptoms, and myalgia,

If, at any time, the patient withdraws consent to participate in the study, he/she will be removed from the study. In such event the investigator will carefully consider whether the patient's withdrawal of consent is due to an adverse event, and if so, record the adverse event as the reason for withdrawal.

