## Memorial Sloan-Kettering Cancer Center IRB Protocol

**IRB#: 07-029A(6)**

### 1.0 PROTOCOL SUMMARY AND/OR SCHEMA

Study Population	Patients with Recurrent Extramammary Paget's Disease (EMPD)
Study Design	Pilot, prospective cohort study
Therapy	Imiquimod 5% Cream applied T.I.W.
Duration of Therapy	12 weeks
Assessment of Response	a. Clinical assessment of before and after photographs by an independent reviewer b. Non-blinded histologic assessment of baseline biopsies and post therapy excisional biopsies 4 weeks after end of treatment
Number of evaluable subjects required	20
Target sample size	Assuming a 15% dropout rate, target sample size is 17

This is a pilot study of the use of a topical immunomodulatory agent, imiquimod, for the treatment of recurrent Extramammary Paget's disease (EMPD). In this protocol we will assess the clinical and histologic effects of topical imiquimod on recurrent EMPD.

Imiquimod 5% cream (Aldara, 3M Pharmaceuticals, St Paul, Minnesota) is an FDA approved safe and effective treatment of anogenital warts, superficial basal cell carcinoma, and actinic keratoses.i

Imiquimod has been demonstrated to induce cytokines that promote a TH1 immune response following both systemic and topical administration.ii The induced cytokines include alpha interferon, gamma interferon, and interleukin 12. The specific mechanism of action by which imiquimod eliminates warts, basal cell carcinoma, and actinic skin cancers is unknown.

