### 10.0 EVALUATION DURING TREATMENT/INTERVENTION

The patient will be seen in clinic at approximately six week intervals during treatment for examination (e.g. week 6 visit will be completed between 35-49 days, week 12 visit between 77-91 days, and week 16 visit between 105-119 days after baseline). Punch biopsy and photography will be performed at the baseline and 12 week visit. The lesion will be assessed after the initial 12 weeks of therapy by visual inspection by the treating physician. Photodocumentation of the area will also be performed at this time. If the lesion is still present, repeat punch biopsy with histologic assessment will be performed (week 12). If the lesion is still present after the initial 12 weeks of therapy, the treating physician will recommend excision of the lesion four weeks following completion of therapy (week 16) to permit resolution of treatment associated inflammation. During this four week time period, the patient will not use imiquimod 5% cream. Any lesion progressing to a clinical appearance suspicious for evolving adenocarcinoma will be excised prior to study completion. The patient will have a follow-up exam 6 weeks after excision and then every 3 months for at least 2 years. If no lesion is present or the patient refuses surgical excision at week 16, the patient will return for follow-up exams every 3 months for at least 2 years. The treating physician will continue to offer surgical excision at any later point during follow-up if the lesion is still present.

**IRB  
PB**

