## Memorial Sloan-Kettering Cancer Center IRB Protocol

**IRB#: 07-029A(6)**

FUNGAL INFECTION*	11%	3%	2%	1%
SYSTEMIC REACTIONS:				
Headache	4%	3%	5%	2%
Influenza-like symptoms	3%	2%	1%	0%
Myalgia	1%	0%	1%	1%

\*Incidences reported without regard to causality with imiquimod

Remote site skin reactions were also reported in patients treated three times weekly with imiquimod 5% cream. The severe remote site skin reactions reported for females were erythema (3%), ulceration (2%), and edema (1%); and for males, erosion (2%), and erythema, edema, induration, and excoriation/flaking (each 1%).

Adverse events judged to be possibly or probably related to imiquimod and reported by more than 1% of patients include: Application Site Disorders: Burning, hypopigmentation, irritation, itching, pain, rash, sensitivity, soreness, stinging, tenderness; Remote Site Reactions (bleeding, burning, itching, pain, tenderness, tinea cruris); Body as a Whole: fatigue, fever, influenza-like symptoms; Central and Peripheral Nervous System Disorders: headache; Gastro-Intestinal System Disorders: diarrhea; Musculo-Skeletal System Disorders: myalgia.

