### 12.0 CRITERIA FOR THERAPEUTIC RESPONSE/OUTCOME ASSESSMENT

The biopsied lesion will be the focus of the histologic assessment. All biopsies will be routinely sectioned and stained (H&E). Photographs will be obtained by the treating physician. Standardized 1:1 fixed distance photography will be performed with a contact camera with a built in light source to ensure standardized images. Millimeter scales will be included in each image to ensure spacial standardization.

Clinical response will be assessed by comparison of pairs of clinical photographs obtained at study completion and baseline. Pairs of photographs will be graded as:

- Complete response = reversion to clinically normal appearing skin.
- Partial response = 50% or greater reduction in diameter of affected skin.
- Progression = 50% or greater increase in diameter of affected skin.

Primary histologic evaluation will entail quantification of the number of involved areas /mm^2 that have Paget's cells. Histologic response will be graded as:

- Complete response = No evidence of Paget's cells
- Partial response = ratio of involved areas/mm^2 in post-treatment biopsy specimen/ pre-treatment biopsy specimen < 50%
- Progression = ratio of involved areas/mm^2 in post-treatment biopsy specimen/ pre-treatment biopsy specimen > 150%

We recognize the subjective nature of determining "significant" changes in appearance of the skin lesion. This problem, common to many dermatology studies, has defied a standardized technologic solution to date. We will use the method that is similar to that employed by a recently published study evaluating the effects of imiquimod on dysplastic nevi.xx In this study, Junctional lesional cells were counted in multiple high power fields and reported as lesional cells/mm^2 and lesional cell

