### 14.0 BIOSTATISTICS

The purpose of this pilot study is to assess the clinical and histologic effects of a topical immunomodulatory agent, imiquimod, on extramammary Paget's disease (EMPD). This is a multicenter study in which the patient and the pathologist will not be blinded to treatment status. Photographs obtained before and after treatment will be evaluated by an independent reviewer. The institutions involved in this study include: Memorial Sloan-Kettering Cancer Center in New York City, NY (MSKCC), and Ohio State University College of Medicine (OSUMC) in Columbus, Ohio.

Twenty patients will be accrued onto this study. It is unknown how patients will respond to this topical treatment and 20 patients is the maximum number of patients that can be accrued in a reasonable time period. Assuming a drop out rate of 15% our target sample size is 17. At the end of this study, we hope to estimate a response rate with a 95% confidence interval  $\pm$  24 % based on 17 patients. Approximately 7 patients are diagnosed a year with EMPD at MSKCC and approximately 1-2 patients a year from OSU. From this we expect to accrue 5-8 patients per year until 20 patients are accrued on study (approximately 3 years). At the end of the study, descriptive statistics will be performed to evaluate the effectiveness of imiquimod therapy on extramammary Paget's disease patients.

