##### **Source Documentation**

Source documentation refers to original records of observations, clinical findings and evaluations that are subsequently recorded as data into CRFs. Relevant source documentation to be submitted throughout the study includes:

- MD office visit notes
- Pathology reports
- Photographs
- Clinical assessment forms
- Grade 3-5 toxicities/adverse events not previously submitted with SAE Reports

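### Section 13 makes three systemic symptoms a reason to leave the study rather than to stop imiquimod, so week-12 outcomes may be lost in a way linked to toxicity

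*Combined protocol and SAP*

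**What the plan says.** Section 13.0 gives the action: "Patients who have unacceptable toxicities will be removed from the study". It then gives the definition: "Unacceptable toxicities consist of headache, influenza-like symptoms, and myalgia". In the text available the definition ends on a comma and a new paragraph follows. No grade, duration or relation to the drug is attached.

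Two other places mention severity, but neither qualifies the removal rule. The source documentation list in Section 16.1.0 asks sites to submit "Grade 3-5 toxicities/adverse events not previously submitted with SAE Reports". Section 17.2 asks for severity and relationship in serious adverse event reports.

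The outcome depends on assessments late in the study. Section 12.0: "Clinical response will be assessed by comparison of pairs of clinical photographs obtained at study completion and baseline". Section 10.0: "Punch biopsy and photography will be performed at the baseline and 12 week visit". The schedule table in Section 10.0 shows no other photograph after baseline. Examinations continue every 3 months for at least 2 years.

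Section 14.0 plans a confidence interval for the response rate "based on 17 patients", after 15% dropout from 20 accrued. The Section 1.0 table gives 20 against "Number of evaluable subjects required". Neither section says how a patient removed before week 12 counts in the response rate.

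**The concern.** Stopping a drug and leaving a study are different events. A patient who stops the cream at week 5 because of flu-like symptoms can still be photographed and biopsied at week 12. A patient who has been removed from the study has no assessment described for her. The loss would be informative if tolerance and response are related. That is possible with an immune response modifier, but the documents do not establish it.

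The rule also sits oddly beside Section 11.0, where a severe local skin reaction leads to washing off the cream and resuming once the reaction subsides. There the patient stays on study.

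At stake are a few outcomes in a study that cannot easily replace them, since Section 14.0 calls 20 the most that can be accrued in a reasonable time. Two sites must also apply the same rule alike. The two-year follow-up is exposed too, and Section 11.0 says progression to invasive carcinoma cannot be excluded.

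**Working it through.** **1. The plan's own figures.** From Section 14.0: 20 accrued, 15% dropout, 17 for analysis, half-width 24 points.
- 20 × (1 − 0.15) = 17.
- 1.96 × √(0.25/17) = 0.238, or 23.8 points. Both figures reproduce.

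**2. How many patients could meet the rule.** Section 11.0 gives rates for headache, influenza-like symptoms and myalgia. For women they are 4%, 3%, 1% on imiquimod (n = 117) and 3%, 2%, 0% on vehicle (n = 103). Women's rates are used because Section 6.1 recruits through Gynecology outpatient services. The overlap between symptoms is not given, so the share with at least one lies between the largest single rate (full overlap) and the sum (no overlap).
- Imiquimod: 4% to 4 + 3 + 1 = 8%. Expected among 20: 0.8 to 1.6.
- Vehicle: 3% to 3 + 2 + 0 = 5%. Expected among 20: 0.6 to 1.0.
- Chance of at least one on imiquimod: 1 − 0.96^20 = 56% to 1 − 0.92^20 = 81%.
- The same at vehicle rates: 1 − 0.97^20 = 46% to 1 − 0.95^20 = 64%.

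The vehicle figures suggest that many of these symptoms could be background. That comparison is itself rough, because one percentage point is about one patient in each group.

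**3. Precision.** The dropout allowance is 20 − 17 = 3 patients.
- Chance that this rule alone removes four or more: Binomial(20, 0.04) gives 0.7%; Binomial(20, 0.08) gives 7.1%.
- If these removals came on top of the 15%: 20 × (1 − 0.15 − 0.04) = 16.2 and 20 × (1 − 0.15 − 0.08) = 15.4 patients, with half-widths of 24.3 and 25.0 points. This may double-count, since the 15% may already include them.

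**4. Possible bias.** Let f be the share removed, p the response rate in completers and q the rate that removed patients would have shown. If removed patients are left out, the reported rate is p and the rate over all treated patients is (1 − f)p + fq. The overstatement is p − [(1 − f)p + fq] = f(p − q).
- q = p: 0 points.
- p = 50%, q = 0: 0.04 × 50 = 2.0 to 0.08 × 50 = 4.0 points.
- p = 83% (five of six, the meeting abstract cited in Section 1.0), q = 0: 3.3 to 6.7 points.

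**5. Cost of counting unassessed patients as non-responders.** If all of them are unassessed and would in fact have responded like completers, the rate is understated by f × q: 2.0 to 4.0 points at 50%, and 3.3 to 6.7 points at 83%.

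**The case against.** The strongest answer is that the rule may be narrower than its literal reading. The words unacceptable and toxicities can imply clinical judgement and a drug effect. Section 11.0 names the same symptoms in a list introduced as "Adverse events judged to be possibly or probably related to imiquimod and reported by more than 1% of patients include", so Section 13.0 may simply be naming which systemic drug effects count. The sentence may also have lost its ending when the file was read. A reader might infer that any mild or unrelated headache must end participation, and so that a removal is more likely than not. The documents do not settle that. The verb used in the definition favours the literal reading, but the 56% to 81% chance assumes that every symptom report leads to removal. The only discontinuation rate given is 1.2% (4 of 327), for local reactions.

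A reader might also infer that the response rate will be biased upward. The documents do not support that either. Section 14.0 neither excludes removed patients nor includes them, nothing says that they respond less, and no section forbids a photograph at removal. Surgery is to be offered to all study patients (Section 17.0), so some histology could still exist, although whether it would be collected after removal is not stated.

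A cautious systemic-toxicity rule is a legitimate clinical choice, and a grade 3 threshold is not a statistical matter. Section 16.3.2 allows deviations, but only case by case and with prior approval.

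What remains is that the stated consequence is removal from the study, and that no section keeps the scheduled outcome assessments afterwards. Neither depends on the missing words or on the symptom rates.

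**Conclusion.** The point holds as a low-cost improvement, not as a threat to the study. Following Section 13.0 as written can lose outcomes for a reason linked to toxicity, and nothing elsewhere in the plan prevents it. The effect is about 1 to 2 patients of 20 at most in expectation, and a worst case of 2.0 to 6.7 points on the response rate, against a planned half-width of 23.8 points. Planned precision is essentially unaffected.

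These sizes rest on stated assumptions: symptom rates from other conditions apply to this disease; every symptom report leads to removal; every removal loses the outcome; and, for the bias, removed patients are excluded and none would have responded. If any of these fails only in part, the effect is smaller. If removed patients respond like completers, it is zero.

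**What to change.** Amend Section 13.0 so that these toxicities stop imiquimod and do not end study participation. For patients who still consent, keep the week-12 photograph, punch biopsy and follow-up visits already in the schedule.

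In Section 14.0, state that the response rate will be reported over all treated patients, with those not assessed counted as non-responders, and show the assessed-only rate beside it.

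The sponsor should also confirm whether the printed definition is complete and whether a severity or relatedness condition was meant. The threshold should be set by the clinical team.

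The cost is one amendment paragraph, with no extra visits. The headline rate may come out slightly lower, and it would be understated (step 5 above) if unassessed patients had in fact responded. That is why keeping the week-12 assessment matters more than the counting rule.

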### 14.0 BIOSTATISTICS

The purpose of this pilot study is to assess the clinical and histologic effects of a topical immunomodulatory agent, imiquimod, on extramammary Paget's disease (EMPD). This is a multicenter study in which the patient and the pathologist will not be blinded to treatment status. Photographs obtained before and after treatment will be evaluated by an independent reviewer. The institutions involved in this study include: Memorial Sloan-Kettering Cancer Center in New York City, NY (MSKCC), and Ohio State University College of Medicine (OSUMC) in Columbus, Ohio.

Twenty patients will be accrued onto this study. It is unknown how patients will respond to this topical treatment and 20 patients is the maximum number of patients that can be accrued in a reasonable time period. Assuming a drop out rate of 15% our target sample size is 17. At the end of this study, we hope to estimate a response rate with a 95% confidence interval  $\pm$  24 % based on 17 patients. Approximately 7 patients are diagnosed a year with EMPD at MSKCC and approximately 1-2 patients a year from OSU. From this we expect to accrue 5-8 patients per year until 20 patients are accrued on study (approximately 3 years). At the end of the study, descriptive statistics will be performed to evaluate the effectiveness of imiquimod therapy on extramammary Paget's disease patients.

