## Memorial Sloan-Kettering Cancer Center IRB Protocol

IRB#: 07-029A(6)

lesion is present or the patient refuses surgical excision at week 16, the patient will return for follow-up exams every 3 months for at least 2 years. The treating physician will continue to offer surgical excision at any later point during follow-up if the lesion is still present.

We will evaluate the clinical and histologic response of recurrent EMPD to treatment. Clinical response will be assessed by a pathologist (non-blinded) and an independent reviewer who will compare clinical photographs obtained at study completion to those obtained at baseline. Lesions will be evaluated based on size as having undergone complete response, partial response, no change, or progression. Histologic evaluation will entail quantifying the number of residual Paget cells following treatment. Side effects and toxicities of therapy will be monitored and recorded.

Presented below is the treatment schema for this prospective cohort.

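### Histology is read unmasked to time point, masking of the photograph reviewer is not specified, and Section 1.0 is inconsistent on who grades clinical response

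*Combined protocol and SAP*

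**What the plan says.** **Histology.** Section 14.0 (Biostatistics) states that "the patient and the pathologist will not be blinded to treatment status". The summary table in Section 1.0 lists "Non-blinded histologic assessment of baseline biopsies and post therapy excisional biopsies 4 weeks after end of treatment". Section 12.0 grades histologic response on involved areas per mm², as a post-treatment to pre-treatment ratio: below 50% is partial response, above 150% is progression, and absence of Paget's cells is complete response.

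**Photographs.** The Section 1.0 table lists "Clinical assessment of before and after photographs by an independent reviewer", and Section 14.0 says "Photographs obtained before and after treatment will be evaluated by an independent reviewer". Section 12.0 adds "Clinical response will be assessed by comparison of pairs of clinical photographs obtained at study completion and baseline". Partial response is a reduction in diameter of at least 50%, and complete response is clinically normal skin. No section describes removing dates, coding images or randomising their order. No section says that the reviewer is told the order either.

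**Who grades clinical response.** The narrative in Section 1.0 says "Clinical response will be assessed by a pathologist (non-blinded) and an independent reviewer who will compare clinical photographs" from completion and baseline. This differs from the table in the same section and from Section 14.0, which name the independent reviewer only.

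**Subjectivity.** Section 12.0 has a caveat that begins "We recognize the subjective nature of determining" and goes on to name the appearance of the skin lesion. It does not mention the histologic count.

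**Precision.** Section 14.0 plans 20 patients, 15% dropout, 17 evaluable, and a 95% confidence interval of ±24% for the response rate.

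**The concern.** There is no comparison group, so the before/after reading is the whole evidence of effect. Section 16.4.2 calls therapeutic efficacy a primary objective. A reader who knows which specimen or image is post-treatment, and expects improvement, may resolve borderline cases in favour of response: a ratio or diameter change near 50%, or a few doubtful cells. In a controlled trial part of that tendency would appear in both arms and cancel. Here it goes straight into the response rate, and the confidence interval does not reflect it.

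The inconsistency in Section 1.0 adds a separate problem. If the pathologist also grades clinical response, a reader declared unblinded contributes to both endpoints, and the plan has no rule for disagreement between the two graders.

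**Working it through.** **1. The plan's own figure.** Inputs from Section 14.0: 20 accrued, 15% dropout, 95% confidence.

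- Evaluable: 20 × (1 − 0.15) = 17.
- Normal-approximation half-width at a rate of 50%: 1.96 × √(0.5 × 0.5 / 17) = 0.238, or 24 points after rounding.

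The stated ±24% is reproduced. The formula contains binomial sampling variation and no term for misreading.

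**2. Weight of one reading.** 1/17 = 5.9 points. Two cases give 11.8, three 17.6, four 23.5.

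**3. Effect of an assumed upgrade rate.** Let p be the true response rate and f the share of true non-responders read as responders, with no error in the other direction. The expected reading is q = p + (1 − p) × f. For p = 0.5 and f = 0.2, q = 0.5 + 0.5 × 0.2 = 0.60.

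Coverage is the probability that the exact (Clopper-Pearson) 95% interval contains p when the observed count is binomial(17, q). It is the sum of the probabilities of all counts x from 0 to 17 whose interval contains p.

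| True rate p | f = 0: coverage | f = 10%: reading, coverage | f = 20%: reading, coverage | f = 30%: reading, coverage |
|---|---|---|---|---|
| 30% | 96.8% | 37%, 94.0% | 44%, 83.7% | 51%, 65.5% |
| 50% | 95.1% | 55%, 93.2% | 60%, 87.1% | 65%, 76.5% |
| 70% | 96.8% | 73%, 96.0% | 76%, 93.8% | 79%, 89.9% |

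The values of p and f are assumptions. The documents give no misreading rate and no target response rate. The effect is small at 10% upgrading, and it is larger when the true rate is low because there are more non-responders to upgrade.

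**4. Who grades clinical response.**

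- Section 1.0 table: independent reviewer.
- Section 1.0 narrative: non-blinded pathologist and independent reviewer.
- Section 14.0: independent reviewer.

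The narrative is the outlier. The sentence before it speaks of clinical and histologic response together, so two assessors of two endpoints may have been merged into one sentence.

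**The case against.** **Tempting stronger readings.**

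- A reader might infer that both endpoints are read with the time point known. The documents say so only for histology. The before/after wording for photographs suggests an open comparison, but the reviewer's masking is unspecified.
- A reader might take the Section 1.0 narrative as the settled plan. The table and Section 14.0 contradict it, so it has to be reconciled before it can count as a second grading scheme.
- A reader might apply the Section 12.0 caveat on subjectivity to histology. It covers skin appearance only.
- A reader might choose four upgraded cases, taking 8/17 (47%, exact interval 23–72%) to 12/17 (71%, 44–90%), a shift of nearly the whole ±24%. That requires misreading 4 of 9 non-responders (44%), which nothing in the documents supports.

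**Existing safeguards.** Section 12.0 specifies fixed-distance photography with a built-in light and millimetre scales. The photograph reviewer is independent, and Section 16.4.2 makes responses subject to an institutional review committee. These help. However, standard images do not hide their order, and independence is not masking. The committee is not said to be masked, and the materials listed for it are radiology, laboratory reports and possibly marrow samples.

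**Declared choice.** Unmasked histology is stated openly in a 20-patient descriptive pilot with no test or success threshold. That is fair: it contradicts nothing in the plan and does not invalidate the study. Complete response probably also leaves less room for judgement than the 50% cut-points.

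**Masking may fail.** An excision can be recognised beside a 3 mm punch, treatment inflammation can reveal a week-12 specimen or image, and a clinically normal image can give away the order of a pair. This stands. It limits what masking achieves but does not remove the reason to use it where it can work.

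**Conclusion.** The point holds in this form: histology is explicitly unmasked, masking of the photograph reviewer is not stated, and Section 1.0 conflicts with itself and with Section 14.0 on who grades clinical response. As written, the plan leaves a reader bias that could be reduced and that the ±24% interval does not cover.

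Its size cannot be derived from the documents. Under assumed one-directional upgrading of 10% to 30% of non-responders, a true 50% rate is overstated by 5 to 15 points on average. Coverage is barely affected at the low end and clearly reduced at the high end. The documents do not show that any such bias will occur, that the photograph reviewer knows the order, or that masking would remove most of the bias. This should be corrected as an inexpensive improvement; it is not a fatal flaw.

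**What to change.** 1. Keep the routine unmasked diagnostic read for patient care.
2. For the histologic endpoint, have the existing pathologist count involved areas per mm² on re-labelled slides in random order. This is chiefly useful for the baseline versus week-12 punch comparison, where specimen type does not reveal the time point.
3. Give the existing independent reviewer each photograph pair with dates removed and order randomised. For each image the reviewer records the diameter and whether the skin is clinically normal.
4. The research study assistant then decodes both sets and applies the Section 12.0 categories.
5. Reconcile the Section 1.0 narrative with its table and with Section 14.0, so that the independent reviewer alone grades clinical response. State in Sections 12.0 and 14.0 what each reader is masked to.

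**Cost.** One batch re-read and some re-labelling, using material and staff already in the study, with no added patients, procedures or readers. The documents give no cost, and the number of slides is not fixed: Section 1.0 allows more than one biopsy, one sentence in Section 10.0 ties the repeat punch to a lesion still being present, and excision is only recommended.

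**Downside.** Masking is partial for the reasons given above. The report should say so and describe the bias as reduced.

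### The clinical response rate has no defined denominator or scoring rule for patients removed or excised early, and the only base Section 14 gives leaves them out

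*Combined protocol and SAP*

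**What the plan says.** Section 14 (Biostatistics) accrues 20 patients and continues: "Assuming a drop out rate of 15% our target sample size is 17". It attaches the response rate and a 95% interval of plus or minus 24 points to 17 patients, and otherwise promises only descriptive statistics. The Section 1 summary table puts 20 against "Number of evaluable subjects required" and gives 17 as the target sample size, so its labels do not match Section 14.

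Section 12 states: "Clinical response will be assessed by comparison of pairs of clinical photographs obtained at study completion and baseline". The schedule in Section 10 places photography at baseline and week 12 only.

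Three routes in Section 13 end participation:
- Invasive carcinoma: "with correlating histology demonstrating invasive carcinoma during the study, the patient will be removed from the study".
- Toxicity: "Patients who have unacceptable toxicities will be removed from the study". The toxicities named are headache, influenza-like symptoms and myalgia, with no grade attached.
- Withdrawal: "If, at any time, the patient withdraws consent to participate in the study, he/she will be removed from the study".

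Section 10 adds early excision: "Any lesion progressing to a clinical appearance suspicious for evolving adenocarcinoma will be excised prior to study completion".

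No section names an analysis set, gives a response score to a patient without the post-treatment assessment, or asks for a photograph at early removal.

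**The concern.** The reasons for leaving early are not neutral with respect to response. Invasive carcinoma on treatment is the clearest failure of the drug, and stopping for toxicity is a failure of another kind. A patient who leaves by either route before week 12 has no photograph pair and so no clinical grade. If the rate is then taken over those who have a grade, likely failures leave the denominator and the estimate rises.

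Section 16.4.2 calls therapeutic efficacy a stated primary objective, so this rate is the trial's main result, and there is no comparator arm to offset a bias in it. With 20 patients, one or two removals move the figure visibly. Because the denominator is not fixed beforehand, it could be chosen once the outcomes are known.

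**Working it through.** **Inputs.** 20 accrued, 15% drop-out, 17 remaining and plus or minus 24 points (Section 14). No response rate is assumed there, so I use 50% (the widest case) for precision and 6, 10 or 14 responders for the shift. The documents give no number of early removals in this disease. I assume 1 to 3, where 3 is the full drop-out allowance for all reasons.

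**The plan's own figure.**
- 20 x (1 - 0.15) = 17.
- Wald half-width = 1.96 x sqrt(p(1 - p)/n). At p = 0.5 and n = 17: 1.96 x sqrt(0.25/17) = 23.8 points, which reproduces the stated 24.
- At n = 20: 1.96 x sqrt(0.25/20) = 21.9 points, which does not. The stated precision therefore rests on 17.

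**Shift when k removed patients did not respond and are left out.** With r responders, the excess is r/(20 - k) - r/20.

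| Responders | All 20 | k = 1 | k = 2 | k = 3 |
|---|---|---|---|---|
| 6 | 30.0% | 31.6% (+1.6) | 33.3% (+3.3) | 35.3% (+5.3) |
| 10 | 50.0% | 52.6% (+2.6) | 55.6% (+5.6) | 58.8% (+8.8) |
| 14 | 70.0% | 73.7% (+3.7) | 77.8% (+7.8) | 82.4% (+12.4) |

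Exact 95% intervals for the middle row: 10/20 gives 27.2% to 72.8%; 10/17 gives 32.9% to 81.6%.

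**Reverse direction.** Take 10 responders among 17 and 3 removals, and suppose 1, 2 or 3 of those removed had in fact responded. The true rate is then 11/20 = 55.0%, 12/20 = 60.0% or 13/20 = 65.0%, against 10/17 = 58.8%. The 17-patient figure is 3.8 points too high in the first case, and 1.2 and 6.2 points too low in the other two.

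**Are 1 to 3 removals plausible?** Section 11 gives headache 4%, influenza-like symptoms 3% and myalgia 1% in women on imiquimod three times a week. These are the toxicities named in Section 13. Depending on overlap, 4% to 8% of patients had at least one, or 20 x 0.04 = 0.8 to 20 x 0.08 = 1.6 patients if every such event led to removal. Those women were other patients in other studies, so this is an illustration and not a prediction.

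**The case against.** The strongest reply is that 17 is a planning figure. Allowing for drop-out when projecting precision does not choose an analysis set, and Section 1 lists 20 as evaluable. This stands. A reader might infer that the protocol declares a completers-only analysis, but it does not; it leaves the set undefined.

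The gap is also mainly in the clinical endpoint. Removal for carcinoma requires histology, and an early excision yields a specimen, so those patients may be gradable under the histologic criteria in Section 12. It would be too strong to say they cannot be scored at all.

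The effect is modest. The study is descriptive, with no test or go/no-go threshold, and every shift in the table is below 24 points. A report that lists responders, removals and reasons would let a reader compute either rate. That is true, but the plan does not require such a report, and the interval describes sampling error, not the effect of leaving failures out.

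Finally, non-responder scoring is a convention. A patient removed for headache has not shown that the lesion failed to respond, so the all-treated rate mixes tolerability with activity. If all 3 removed patients had responded, it would give 10/20 = 50.0% against a true 65.0%, further off than 58.8%. That is why the evaluable rate belongs beside it.

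**Conclusion.** The point holds: the denominator and the scoring of patients without a completion photograph are unstated, and the only base Section 14 attaches to the rate would drop early removals. The clinical response rate would then probably be too high, by 2.6 to 8.8 points with 10 responders and 1 to 3 removals. Across 6 to 14 responders the range is 1.6 to 12.4 points. This assumes that the removed patients did not respond. That is reasonable for invasive carcinoma, less certain for toxicity and open for withdrawal.

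Two further inferences are not supported. Moving from 23.8 to 21.9 points is not a gain in precision: patients scored by rule add no information on lesion response, and the interval narrows because the rate has been redefined. The 1.2% (4/327) discontinuation rate in Section 11 does not measure expected removals either. It covers local skin reactions, which the protocol manages by pausing and resuming treatment and which are not among the toxicities in Section 13.

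Severity is low to moderate for a descriptive pilot, and the remedy is cheap.

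**What to change.** Add to Section 14:

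1. The primary clinical response rate is responders divided by all patients who applied at least one dose. Patients removed early, excised before the week-12 assessment or lacking that assessment for any reason count as non-responders.
2. The rate in evaluable patients is reported beside it, with the number of removals and the reason for each.
3. The interval for the all-treated rate is about plus or minus 22 points on 20 patients, stated as a consequence of the redefined rate. Align the labels for 20 and 17 in Section 1.
4. For histology, any biopsy or excision specimen obtained at early removal is graded. A clinically cleared patient without a week-12 biopsy is not a non-responder by default. This is needed because one sentence in Section 10 makes that biopsy conditional ("If the lesion is still present, repeat punch biopsy with histologic assessment will be performed (week 12"), while the schedule lists it for everyone.

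The cost is a few sentences, with no new visits, patients or data. The downside is that the headline rate may be lower, and that for patients removed for toxicity or unrelated withdrawal it combines tolerability with activity.
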